7.2 Analysis Populations

The Safety Population includes all subjects who receive any amount of investigational product. Demographics, safety endpoints, IM, PD, and disease activity will be summarized based on the Safety Population. Additional analysis populations may be defined as needed.

7.3 Endpoints

7.3.1 Primary Endpoint

The primary objective of this study is to evaluate the long-term safety and tolerability of IV MEDI-546 in adult subjects with moderately-to-severely active SLE. The safety and tolerability of MEDI-546 will be assessed primarily by summarizing treatment-emergent AEs (TEAEs) and treatment-emergent SAEs (TESAEs). Other variables used for the safety assessments will include serum chemistry, hematology, urinalysis, vital signs, physical examination, ECG, and concomitant medications.

All TEAEs and TESAEs will be summarized by system organ class and preferred terms, by severity and relationship to investigational product. No formal statistical testing will be performed. Other safety variables as well as their changes from baseline (if applicable) will be summarized descriptively.

7.3.2 Secondary Endpoint

The secondary objective of this study is to evaluate the IM of MEDI-546. Immunogenicity results will be analyzed by summarizing the number and percentage of subjects who develop detectable ADAs. The titer of ADAs will also be summarized. The association of ADA titers with AEs, PK, SLEDAI-2K, and PD markers will also be evaluated.

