3.6 Pharmacodynamic Endpoint and Analyses

3.6.1 Type I IFN Signature

The 21-gene type I IFN signature in whole blood will be used as a PD marker. The gene signature and the neutralization levels will be summarized by visit. Subgroup analysis of 21-gene type I IFN signature will be performed based on ADA status (positive vs negative).

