3.8.7 Subgroup Analyses

The treatment emergent AEs and SAEs will be summarized by 4-gene IFN signature (IFN high vs IFN low) and ADA status (positive vs negative).

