3.9 Immunogenicity

The IM results will be analyzed by summarizing the number and percentage of subjects who develop positive ADA. A descriptive summary of actual ADA titers by visit will also be provided.

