3.10 Pharmacokinetics

The PK components of the clinical study report will be generated and reported by MedImmune's Clinical Pharmacology & DMPK group.

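### The protocol's only secondary endpoint relates ADA titer to adverse events and PD, but the SAP's readable AE and PD analyses use only ADA positive/negative status

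*Protocol*

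**What the plan says.** Protocol 7.3.2 opens with "The secondary objective of this study is to evaluate the IM of MEDI-546". No other secondary objective or endpoint is listed. The endpoint has three parts: how many subjects develop ADA, a summary of titers, and the association, worded as "The association of ADA titers with AEs, PK, SLEDAI-2K, and PD markers will also be evaluated". The study abstract makes the same commitment, and Protocol 7.1 leaves the analysis details to the SAP.

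The SAP covers the three parts as follows:

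- **Incidence and titer (SAP 3.9).** "The IM results will be analyzed by summarizing the number and percentage of subjects who develop positive ADA", followed by "A descriptive summary of actual ADA titers by visit will also be provided".
- **Adverse events (SAP 3.8.7).** "The treatment emergent AEs and SAEs will be summarized by 4-gene IFN signature (IFN high vs IFN low) and ADA status (positive vs negative".
- **PD (SAP 3.6.1).** "Subgroup analysis of 21-gene type I IFN signature will be performed based on ADA status (positive vs negative".
- **PK (SAP 3.10).** "The PK components of the clinical study report will be generated and reported by MedImmune's Clinical Pharmacology & DMPK group".
- **SLEDAI-2K.** The efficacy section, SAP 3.4, is only partly visible; its numbering passes straight to 3.4.4.

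**The concern.** The protocol chose titer as the measure to be related to AEs and PD. For both, the SAP substitutes a yes/no status and gives no reason. Titer is still tabulated, but the tabulation stands alone. Followed as written, the SAP leaves part of the only secondary endpoint undelivered.

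Two groups, positive and negative, cannot show whether outcomes change with the level of response among positives. If an effect on safety or on PD neutralisation were concentrated at higher titers, averaging it with low-titer subjects would make it look smaller. Infusion, hypersensitivity and anaphylactic reactions are a named event of special interest (Protocol 6.1.3.5, SAP 3.8.2), but SAP 3.8.7 plans no separate display of that AESI by ADA at all.

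**Working it through.** **1. Commitment against plan.**

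| Protocol 7.3.2 association | Readable SAP analysis | Titer used? |
|---|---|---|
| Titer and AEs | 3.8.7, TEAEs and SAEs by status | No |
| Titer and PD | 3.6.1, 21-gene signature by status | No |
| Titer and PK | 3.10, reported by another group | Cannot be judged |
| Titer and SLEDAI-2K | 3.4, partly not visible | Cannot be judged |

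Safety subsections 3.8.1 to 3.8.7 run without a gap in numbering, and the AE and PD sentences are fully readable. The first two rows therefore do not depend on missing text. The SAP version history lists only a layout change and a change of medication dictionary, so it does not explain the use of status.

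**2. The plan's own figure.** SAP 2.4 starts from 307 randomised and assumes a 20% loss: 307 × (1 − 0.20) = 245.6, consistent with its approximate 240. It serves here only as a denominator.

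**3. Size of a possible dilution (assumed inputs).** Let h be the share of ADA-positive subjects with high titers. Suppose high-titer subjects have 3 times the risk of ADA-negative subjects and low-titer subjects have no excess. The positive-versus-negative ratio is then 3h + 1 × (1 − h). On the difference scale, if high-titer subjects carry an excess of D percentage points, the status split shows h × D. Taking 20% AE risk without the excess and 60% with it gives D = 40; 20% and 40% gives D = 20.

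| h | Ratio shown (true 3.0) | Difference shown, D = 40 | Difference shown, D = 20 |
|---|---|---|---|
| 10% | 1.2 | 4 points | 2 points |
| 20% | 1.4 | 8 points | 4 points |
| 25% | 1.5 | 10 points | 5 points |
| 50% | 2.0 | 20 points | 10 points |

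If instead every positive subject has the threefold risk, the ratio is 3h + 3(1 − h) = 3.0 and nothing is diluted. The dilution therefore depends on low-titer subjects having less excess risk.

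**4. Likely cell sizes (assumed range).** With N = 240 and 2% to 20% ADA-positive, there are 240 × 0.02 = 4.8 (about 5) to 240 × 0.20 = 48 positive subjects. With 10% to 50% of these high-titer, that is 4.8 × 0.10 ≈ 0.5 to 48 × 0.50 = 24 high-titer subjects.

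**5. Available data.** The schedule tables place ADA and 21-gene samples at the same scheduled visits: Day 1; Weeks 12, 24, 36 and 48; every 24 weeks from Week 72; Week 156; and Visits 41 and 43.

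**6. Timing.** Nonserious AEs are generally recorded only in the first year (Protocol 6.1.1, SAP 3.8.4). A subject who completes treatment has 4 scheduled post-baseline ADA samples in that year (Weeks 12, 24, 36, 48) and 7 later (Weeks 72, 96, 120, 144, 156, Visits 41 and 43). So 7 of 11 chances for a peak titer fall after routine nonserious AE capture has ended.

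**The case against.** **The information is not lost.** A reader might infer that a titer effect could not be seen at all. The documents do not support that. Titers are collected and summarised by visit, SAP 3.1 plans subject-level listings, and a large effect could still appear in diluted form. Table templates sit in a separate programming plan that is not public. This stands, so the point is limited to what the AE and PD summaries described in the SAP can show.

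**Nothing in the documents says effects sit at high titers.** This also stands. If being positive is what matters, status is the more stable summary. The figures in the working illustrate a mechanism and are not estimates for this trial. The mismatch does not need the mechanism, because the protocol itself named titer.

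**Cells may be too small.** At the low end of the assumed range a titer table is close to a listing, and no formal safety testing is planned (Protocol 7.3.1), so no inference changes. That argues for an individual-subject display, not for leaving titer out.

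**A whole-study peak-titer split would mislead.** It is the obvious remedy, but it has three faults. A peak in year 2 or 3 could be used to explain an AE in year 1. Subjects treated for longer have more samples and so more chances of a high peak. Every subject comes from a parent study in which some received MEDI-546, so Day 1 positives need a rule. The fix has to avoid all three.

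**Conclusion.** The point holds for two of the four associations named in Protocol 7.3.2. For AEs and PD, the readable SAP replaces titer with status and does not explain why, so the planned summaries cannot show a titer gradient. This follows from the text and needs no assumption.

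That the summaries would also dilute a gradient is conditional on excess risk lying at higher titers. Under the assumed inputs a true ratio of 3.0 would show as 1.2 to 2.0.

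A reader might also infer that the SAP drops the titer association altogether. The documents do not support that: the PK and SLEDAI-2K parts may be covered in redacted text or by another group, and they are not judged here. The primary safety analysis is not affected.

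**What to change.** - **SAP 3.8.7:** add a descriptive display of TEAEs, SAEs and the infusion/hypersensitivity/anaphylaxis AESI against ADA titer. Use a plot or listing for each ADA-positive subject, or titer categories if numbers allow. Relate each event only to titers measured at or before its onset. Limit the TEAE display to titers from the first-year capture window. Show subjects who were ADA-positive at Day 1 separately.
- **SAP 3.6.1:** show the 21-gene result against the titer at the same visit.
- **SAP 3.9:** state where the associations of titer with PK and SLEDAI-2K are reported.

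If the sponsor prefers status alone for AEs and PD, the SAP should record this as a departure from Protocol 7.3.2 and give the reason.

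The cost is a few sentences of SAP text and a small number of extra displays, with no new samples or visits. The limits are that ADA-positive numbers may be small and that the last titer before an event can be weeks old, because scheduled samples are 12 weeks apart from Day 1 to Week 48 and mostly 24 weeks apart afterwards. The displays are descriptive only.

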7.3.3 Exploratory Endpoints

7.4 Interim Analysis

Although no formal interim analyses of the extension period data are planned, analyses of the accumulating data during the extension period may be performed to assess the ongoing safety and risk/benefit of the study treatment and to assist with Phase 3 planning. The final analysis of extension period data will take place after the last on-study subject completes the extension period follow-up visit or discontinues from the study.

7.5 Sample Size and Power Calculations

7.6 Data Safety Monitoring Board

An independent DSMB is an advisory to the sponsor and will perform evaluations of safety data at specified time points throughout the study in accordance with the DSMB Charter (see Appendix 5) and make recommendations to the sponsor regarding the conduct of the study. At any time during the study, as well as on an ad hoc basis, the DSMB will also review any safety data assessed by the medical monitor to be medically relevant.

8 DIRECT ACCESS TO SOURCE DOCUMENTS

The study will be monitored by the sponsor or designee on a regular basis throughout the study period. During monitoring visits, the investigator will provide direct access to all source documentation relevant to the subject's participation in the study. Source documentation includes, but is not limited to, the subject's clinic and/or office chart, hospital chart, ICFs, treatment notes, laboratory reports, pharmacy records, radiographs, recorded data from automated instruments, and any other records maintained to conduct and evaluate the clinical study. The investigator must also ensure that direct access to study documents be made available for study-related audits, IRB/IEC review, or regulatory inspection.

9 QUALITY CONTROL AND QUALITY ASSURANCE

9.1 Data Collection

As part of the responsibilities assumed by participating in the study, the investigator agrees to maintain adequate and accurate case histories for the subjects treated under this protocol. Case histories include CRFs and supporting data including, but not limited to, signed and dated ICFs, progress notes, hospital charts, nurse's notes, diary cards or other worksheets provided to subjects, laboratory reports, ECG strips, etc.

Subject demographics and key/essential disease baseline characteristics thought to affect outcome, ie, stratification variables and other prognostic factors may be collected, as available, for all subjects who provide written informed consent. For subjects who provided informed consent and were not entered into the study, the reason the subject was not entered, ie, did not meet one or more inclusion criteria, met one or more exclusion criteria, or other (eg, lost to follow-up, consent withdrawn), may also be collected.

9.2 Study Monitoring

The primary source document for this study will be the subject's medical record. If separate research records are maintained by the investigator(s), both the medical record and the research records will be monitored/audited for the purposes of the study.

The investigator and institutions involved in the study will permit study-related monitoring and provide direct access to all study records and facilities. Adequate time and space for monitoring visits should be made by the investigator or other investigator site staff.

The monitor will visit study facilities at periodic intervals, in addition to maintaining necessary contact through telephone, e-mail, and letter, to ensure that the study is conducted

and documented in accordance with the protocol, GCP, and applicable regulations. The monitor will assess subject enrollment and informed consent procedures; investigational product storage, dispensing, administration and accountability; compliance with protocol procedures; completeness and accuracy of data entered onto validated data collection instruments (paper CRF or electronic data screen) against original source documents; the continued acceptability of the facilities and qualifications of the site staff; and the occurrence of AEs/SAEs. All aspects of the study will be carefully monitored for compliance with the protocol, applicable regulatory requirements, GCP, and the site's standard operating procedures.

The monitor will discuss the conduct and progress of the study with the investigator and other site staff. The investigator must cooperate with the monitor to ensure that corrective action is taken to resolve any problems noted in the course of the monitoring, and that the preventative measures are put into place to prevent recurrence of issues. In cases where compliance is not achieved, shipment(s) of investigator and product to the investigator will be discontinued and study participation by that investigator will be terminated.

9.3 Audit and Inspection of the Study

During and after the study, the sponsor or its representative may conduct audits of any data and any facility participating in the study. The investigator and institutions involved in the study will permit such study-related audits and provide direct access to all study records and facilities. The investigator must maintain a comprehensive and centralized filing system of all study-related documentation that is suitable for inspection by the sponsor or its designated monitors, auditors, or regulatory agency representatives. The investigator agrees to participate in audits conducted at a convenient time in a reasonable manner.

Government regulatory authorities may also perform inspections either during or after the study. In the event of an inspection by any regulatory authority, the investigator should promptly notify the sponsor. The investigator agrees to cooperate fully with inspections conducted by regulatory authorities and to allow representatives of the regulatory authority access to all study records. The investigator will forward to the sponsor a copy of any inspection records received.

10 ETHICS

10.1 Regulatory Considerations

The study will be conducted in accordance with ethical principles that have their origin in the Declaration of Helsinki and are consistent with the ICH guidelines on GCP, any applicable

laws and requirements, and any conditions required by a regulatory authority and/or IRB/IEC that approves this study to be conducted in its territory. Good Clinical Practice is defined as a standard for the design, conduct, performance, monitoring, auditing, recording, analysis, and reporting of clinical studies in a way that provides assurance that the data and reported results are credible and accurate, and that the rights, safety, and well-being of study subjects are protected.

Per GCP, the protocol will be reviewed and approved by the IRB or IEC of each participating center prior to study initiation. Serious adverse events regardless of causality will be reported to MedImmune Patient Safety or designee, and the investigator will keep the IRB/IEC informed as to the progress of the study.

The investigator will explain the nature of the study and will inform the subject that participation is voluntary and that the subject can withdraw or be withdrawn from the study at any time. Written informed consent will be obtained from each subject prior to the Day 1 procedures to determine if study eligibility criteria are met. A copy of the signed consent form(s) will be given to every subject, and the original(s) will be maintained with the subject's records.

10.2 Institutional Review Board or Independent Ethics Committee

A list of IRB/IEC members or a Statement of GCP Compliance should be obtained by the investigator and provided to the sponsor.

Any documents that the IRB/IEC may need to fulfill its responsibilities, such as protocol amendments, and information concerning subject recruitment, payment, or compensation procedures, or information from the sponsor will be submitted to the IRB/IEC. The IRB/IEC's written unconditional approval of the study protocol, the ICF(s), and any other written materials to be provided to subjects will be in the possession of the investigator and the sponsor before the study is initiated. The IRB/IEC's unconditional approval statement will be transmitted by the investigator to the sponsor prior to shipment of investigational product supplies to the site. This approval must refer to the study by exact protocol title and number, and should identify the documents reviewed and the date of review.

Protocol modifications or changes may not be initiated without prior written IRB/IEC approval except when necessary to eliminate immediate hazards to the subjects or when the change(s) involves only logistical or administrative aspects of the study. Such modifications will be submitted to the IRB/IEC and written verification that the modification was submitted should be obtained.

The IRB/IEC must be informed by the investigator of ICF changes or revisions of other documents originally submitted for review; serious and/or unexpected adverse experiences occurring during the study (as applicable according to local regulations); new information that may affect adversely the safety of the subjects or the conduct of the study; an annual update and/or request for re-approval; and when the study has been completed.

10.3 Informed Consent

Freely given informed consent will be obtained and documented for all subjects under this protocol (or a subject's legal representative, if the subject is unable to provide informed consent) in accordance with ethical principles that have their origin in the Declaration of Helsinki and are consistent with the ICH guidelines on GCP, any applicable laws and requirements, and any conditions required by a regulatory authority and/or IRB/IEC.

Information should be given in both oral and written form, and subjects or their legal representatives must be given ample opportunity to inquire about details of the study.

The consent form(s) generated by the investigator must be approved by the IRB/IEC and be acceptable to the sponsor. Consent forms must be written so as to be understood by the prospective subject/legal representative. Informed consent will be documented by the use of a written consent form(s) approved by the IRB/IEC and signed and dated by the subject or the subject's legal representative, and by the person who conducted the informed consent discussion. The signature confirms the consent is based on information that has been understood. Each subject's signed ICF(s) must be kept on file by the investigator for possible inspection by the sponsor or its designated monitors, auditors, or regulatory agency representatives. The subject or the subject's legal representative should receive a copy of the signed and dated written ICF(s) and any other written information provided to the subject, and should receive copies of any signed and dated consent form updates and any amendments to the written information provided to subjects.

10.4 Withdrawal of Consent for Continued Study Participation

Data and Samples Obtained for the Main Study

Study data are protected by the use of an SID number, which is a number specific to the subject. The investigator is in control of the information that is needed to connect a study sample to a subject. A subject's consent to the use of data does not have a specific expiration date, but the subject may withdraw consent at any time by notifying the investigator. If consent is withdrawn, any data collected prior to that time may still be given to and used by

the sponsor but no new data or samples will be collected unless specifically required to monitor safety of the subject.

Samples Obtained for Future Research

Samples obtained for future research will be labeled with a sample identification number but will not be labeled with personal identifiers such as the subject's name. A file linking this sample identification number with the SID number will be kept in a secure place at the sponsor with restricted access. If the subject withdraws consent for participating in the future research, this link will allow the sponsor to locate the subject's sample and destroy it. The coding of samples and results is to ensure that these research results are kept confidential by keeping the subject's identity and these results separate.

If the subject consents to have his/her urine or sera samples used for future research, this additional research may not start immediately and may start at any time during the storage period. The subject's sample(s) will be stored by the sponsor with similar samples from other subjects at a secure central laboratory. The subject's samples will not be kept for more than 25 years after the end of the study in which they were collected. If the subject chooses not to allow his/her study samples to be used for future research, the samples will be destroyed by the sponsor once they are no longer required for the main study.

If consent is withdrawn after a sample has been taken but before the subject's sample is sent to the sponsor for future research, the investigator will arrange to have it destroyed. If consent is withdrawn after the subject's sample(s) have been sent to the sponsor for future research, the sponsor and the investigator will ensure that these sample(s) are destroyed unless the sample identification number has been removed and the subject can no longer be linked to any sample(s). However, if the subject's samples have already been used for research, the sponsor is not required to destroy results of this research. In this case only the remaining sample(s) will be destroyed.

